#### Table 1. Participants for lab test

#### Table 2. Participants for field trials

Prima	ary end user	s (SMCI)	Secor	ndary end users ( caregivers)	informal	Secondary (centres)	Control group		
Italy	Switzerland	Norway	Italy	Switzerland	Norway	All pilot sites			
20- 22	20-23	8-10	20-22	20-23	8-10	≥2	≥30 (≥10 per each pilot site)		

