The field trial is a pilot study, that is, a small-scale study, conducted mainly to control whether and how the developed services are perceived useful and usable. The defined qualitative and quantitative key performance indicators (KPI) will be evaluated and used to assess the degree to which engAGE meets the elders' needs, wishes and priorities in all trial sites (i.e. achieving better engagement, better social interaction, and accurate measurement of cognitive decline based on machine learning techniques). The measurements collected from the real-life trials will be elaborated and evaluated, to assess the ecosystem performance and validate the success of the project-developed technologies. The field trial will conduct only a partial evaluation of the effectiveness of services in relation to some dimensions of cognitive status of older people with MCI.

In the following scheme (Fig. 2) the study design is summarized. A certain number of people are recruited for the study, then those who do not meet the criteria or decline the participation are excluded. The remaining participant are randomly assigned to the experimentation group or to the control group. In randomization technique based on a single sequence of random assignments is used. A list of random numbers generated by the computer is used and subject is assigned a number based on their order of inclusion in the study. According to this technique, the 80 subjects are randomly assigned to the

experimentation group or to the control group. Then, for both the groups it has to be taken note of who loose follow up, discontinued intervention, and/or are excluded from analysis.

Figure 2. Field trial - study design

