#### 3.3 Channels of recruitment

To ensure that the right participants are included in the evaluations, each partner must have its own recruitment technique, and ensure that the inclusion criteria mentioned above are met. Several channels are available for this purpose, and everyone is free to proceed in the easiest perceived way. Each pilot site should give priority to those who participated in the laboratory tests

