#### 3.4 Outcomes

In this section the outcomes measured throughout the field trials are reported. The main focus of the engAGE project, and so of the field trial, is the perceived stability of cognitive capabilities of people with MCI. In second place, the acceptance and the usability of the platform, as well as the caregivers' benefits have to be assessed. Thus, the outcomes are the following:

- PRIMARY END USERS (SMCI):
  - Primary outcome: perceived stability of cognitive status (MAC-Q)

- Secondary outcomes: Adherence to intervention, wellbeing, quality of life, acceptance and usability, cost-benefit analysis
- SECONDARY END USERS (INFORMAL CAREGIVERS):
  - Reduction/stability of informal caregiver's burden
  - Improvement of well-being, psychological status
  - Acceptability, usability and affordability of the solution
- TERTIARY END USERS (FORMAL CAREGIVERS):
  - Improving quality of work.

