#### 3.7 Work hypothesis

#### Work hypothesis

In this section, the hypothesis is presented along with solutions to measure the impact on those aspects.

- 1. Is there any improvement in the cognitive status?
  - Comparison of MAC-Q (before and after)
    - between groups (EG Vs CG)
    - o intra-group (EG)
- 2. Is the system usable for people with MCI?
  - Analysis of SUS in the EG
  - Analysis of UTAUT in the EG
  - stratifying for MCI
- 3. Is it the system effective in supporting lifestyle of people with MCI and their carers?
  - Adherence to the system to be assessed technically:
    - $\circ \quad \text{Nr. of interactions}$
    - o Nr. planned activities respected
- 4. And the quality of life of the participants?

- Comparison of QoL and WEMBS (before and after)
  - between groups (EG Vs CG)
  - o intra-group (EG)
- For Carers: Comparison of QoL and ZARIT (before and after)
  - between groups (EG Vs CG)
  - o intra-group (EG)
  - improvement of quality of work for Formal carers (from semi structured interview)
- 5. From semi-structured interview:
  - analysis of single modules' effectiveness/perception;
  - cost-benefit analysis;
  - willingness to pay.

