## 4 Data Management

#### 4.1 Statistical Analysis

The first step of the data analysis will deal with the description of the sample. Continuous variables will be reported as either mean and standard deviation or median and interquartile range on the basis of their distribution (assessed using Kolmogorov-Smirnov test). Categorical variables will be expressed as an absolute number and percentage. Mann-Whitney U tests (for non-normal distribution), or Chi-Square tests (normal or non-normal) will be used to compare the independent and dependent variables between the pre- and post- conditions, in addition to simple descriptive statistics (means, medians and SDs as appropriate).

In order to verify the achievement of the primary endpoint (i.e., MAC-Q), subscales of the questionnaire will be calculated. Means and standard deviation or medians and iqr of the scores will be reported according to their distribution. Correlation coefficients (Pearson for normally distributed variables, Spearman for non-normally distributed variables) of the sub-scales with the other rating scales at each stage of the study and with the main characteristics of the subjects will be calculated to check for potential determinants of higher acceptability.

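### With 80 participants, Table 2's site-specific group sizes are very unlikely to come from the single unstratified randomisation list in section 3.1, and the planned comparison takes no account of site

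*Combined protocol and SAP*

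**What the plan says.** Section 3.1 (Study design) describes simple randomisation: "In randomization technique based on a single sequence of random assignments is used", from computer-generated random numbers, where each "subject is assigned a number based on their order of inclusion in the study". It adds that "the 80 subjects are randomly assigned to the" experimental or control group. It gives no allocation ratio, blocking, stratification or site-specific list.

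Table 2 sets the primary end users at 20-22 in Italy, 20-23 in Switzerland and 8-10 in Norway. The control group is "≥30 (≥10 per each pilot site").

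Section 3.4 names the "Primary outcome: perceived stability of cognitive status (MAC-Q"). Section 3.7 (Work hypothesis) compares MAC-Q before and after, "between groups (EG Vs CG") and within the experimental group. Section 4.1 (Statistical Analysis) says that "Mann-Whitney U tests (for non-normal distribution), or Chi-Square tests (normal or non-normal) will be used to compare the independent and dependent variables". Neither section mentions site or country.

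**The concern.** Section 3.1 and Table 2 describe different trials. A single list applies the same allocation probability everywhere, while Table 2 combined with 80 participants needs roughly 2:1 at two sites and at most 1:1 at the third. One of the two descriptions will not be honoured.

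The consequence depends on which gives way. If the list is followed, the site sizes are missed. If the sizes are enforced, arm becomes associated with country, and sections 3.7 and 4.1 contain nothing to remove that association.

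Country could plausibly matter. Section 3.3 says that "each partner must have its own recruitment technique". Italy and Switzerland draw on neurology, memory and day-care services, and Norway mainly on two municipal day centres. Table 5 marks the MoCA for Italy and Switzerland only.

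**Working it through.** **Inputs.** Total 80 (section 3.1). Experimental group (EG) ranges and control group (CG) minima by site (Table 2). The allocation ratio and site totals are not stated, so all feasible values are examined. The documents give no site difference, so 0.3, 0.5 and 1.0 SD are assumed.

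**1. Reproducing the 80.** EG sums to 20+20+8 = 48 up to 22+23+10 = 55. Adding 30 controls gives 78 to 85, and 50+30 = 80. The total therefore fits if Table 2's primary users and controls are separate groups. If the primary users included controls, the total would be only 48-55.

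**2. Designs that fit both passages.** CG of at least 30 forces EG to be at most 50, and EG of at least 48 forces CG to be at most 32. Enumeration gives 21 integer designs, with six possible site totals (Italy/Switzerland/Norway): 30/30/20, 30/31/19, 31/30/19, 30/32/18, 31/31/18 and 32/30/18.
- EG:CG in Italy and in Switzerland: 20/12 = 1.67 to 22/10 = 2.2.
- EG:CG in Norway: 8/12 = 0.67 to 10/10 = 1.0.
- In every design the Italian and Swiss ratios are each at least twice the Norwegian ratio.

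**3. Chance that one list delivers Table 2.** With a constant probability p of EG, P(all sizes met) is the product over sites of Σ C(n,k) p^k (1−p)^(n−k). The sum runs over k in the site's EG range with n−k ≥ 10. For a list fixed at 50:30, it is Σ C(n1,a)·C(n2,b)·C(n3,c) / C(80,50) over the admissible splits a+b+c = 50.

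| Single list | P(every Table 2 size met) |
|---|---|
| 1:1, best site totals (31/31/18) | 0.0601 × 0.0601 × 0.1669 = 0.06% |
| Best p (0.61), best site totals (31/31/18) | 0.252 × 0.252 × 0.0666 = 0.42% |
| Fixed 50:30, over all six site totals | 1.0% to 1.9% |

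The 1.9% is C(30,20)²·C(20,10)/C(80,50) at 30/30/20. The same formula for lists fixed at 48:32 or 49:31 gives 0.5% to 2.4%.

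The weaker requirement of at least 10 controls at every site is also often missed:
- At 1:1: 0.979 × 0.979 × 0.588 = 56% at 30/30/20 (the maximum), and 0.985 × 0.985 × 0.407 = 39% at 31/31/18. Expected EG in Italy and in Switzerland is then only 15-16, against a target of at least 20.
- At 5:3: 0.742 × 0.742 × 0.177 = 9.8% at 30/30/20 (the maximum), and 0.783 × 0.783 × 0.092 = 5.6% at 31/31/18. Expected Norwegian controls are 18 × 3/8 = 6.75 to 20 × 3/8 = 7.5.

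**4. Bias if Table 2 is enforced and site is ignored.** The size of the bias in a difference of means is (Norway's share of CG − Norway's share of EG) × Δ. Here Δ is the Norway-versus-rest difference in whatever is compared, and Italy and Switzerland are taken as alike.
- Smallest: EG 20/20/10, CG 10/10/10 gives 10/30 − 10/50 = 0.13.
- Largest: EG 20/20/8, CG 10/10/12 gives 12/32 − 8/48 = 0.21.

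| Assumed Δ | Bias over the 21 designs | Two-sided error at nominal 5%, 50:30 designs |
|---|---|---|
| 0.3 SD | 0.04-0.06 SD | 5.3-5.6% |
| 0.5 SD | 0.07-0.10 SD | 6.0-6.6% |
| 1.0 SD | 0.13-0.21 SD | 8.9-11.7% |

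The error rates use a normal approximation, Φ(−1.96−b/SE) + 1 − Φ(1.96−b/SE), with SE = √(1/50 + 1/30) SD. The 5% level is assumed, because section 4.1 states none.

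**5. Variance cost of a site-stratified comparison.** Stratified variance is 1/Σ[EG·CG/(EG+CG)].
- 20:10, 20:10, 10:10: 1/(6.667+6.667+5) = 0.0545, against 1/50+1/30 = 0.0533 pooled (+2%).
- 21:10, 21:10, 8:10: 1/(6.774+6.774+4.444) = 0.0556 (+4%).
- Largest over the 21 designs, 20:10, 20:10, 8:12: 1/(6.667+6.667+4.8) = 0.0551, against 1/48+1/32 = 0.0521 (+6%).

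**The case against.** Several parts of the case on the other side stand.

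- **Table 2 alone does not require 2:1.** Its control numbers are minima. A common 1:1 ratio (20:20, 20:20, 10:10) satisfies it with 100 participants. The conflict needs the 80 of section 3.1 as well. Even with the total left free, though, one constant-probability list meets every size at most 7.6% of the time.
- **A single list does not itself confound arm with site.** A reader might infer that it does. A constant-ratio list that is followed is balanced by site in expectation. The bias arises only if unequal site ratios are imposed and site is then ignored. The documents do not say that sites would override the list.
- **The bias is modest unless sites differ substantially.** If change in MAC-Q is compared, stable country differences in level cancel, and only differences in change count.
- **Missing every range is a strict criterion.** It counts a shortfall of one person as failure. The chance of at least 10 controls per site is a gentler test, and it is still at most 56% at 1:1 and 9.8% at 5:3.
- **This is described as a small pilot** with only a partial evaluation of effectiveness. That limits what is at stake. But participants are still randomised, and the between-group MAC-Q comparison is still planned on the primary outcome.

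Figure 2, which summarises the design, could not be read for this review and may state group sizes or a ratio. Group totals there would not change the single-list text or the Table 2 numbers.

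**Conclusion.** The point holds as an unreconciled conflict between section 3.1 and Table 2, together with a comparison that leaves out site. At 80 participants, a single unstratified list is very unlikely to give the Table 2 sizes: at most 0.42% with any constant allocation probability between 0.30 and 0.80, and 1.0-1.9% with a list fixed at 50:30. Saying that it cannot deliver them would go too far.

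The bias of 0.13-0.21 times the Norway-versus-rest difference is conditional on Table 2 being enforced and site being ignored. Its size in SD units rests on assumed site differences. The whole calculation assumes that Table 2's primary users and controls are separate groups, which is the reading that matches 80.

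A reader might also infer that recruiters could foresee assignments from a list followed in order of inclusion. The documents do not say who holds the list, so they do not support that conclusion.

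**What to change.** Reconcile section 3.1 with Table 2 before the first participant is randomised:

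1. Use a separate randomisation list for each site and state each site's allocation ratio. For example, 20:10, 20:10 and 10:10 meets Table 2 exactly at 80. Alternatively, keep one common ratio and restate the Table 2 sizes to match it.
2. In section 4.1, specify that the EG-CG comparison is stratified by or adjusted for site, for instance a stratified rank test or a model with site as a factor. Separate lists at unequal ratios do not remove the bias without this step.

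The cost is three lists instead of one and a few lines of text. No extra participants are needed. The site-stratified comparison has about 2-4% more variance at 50:30, and at most 6% over all designs that fit both passages.

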#### 3.2 Informed consent and ethical approval

Each pilot site must obtain ethical approval before testing the engAGE platform and services. Moreover, according to the Declaration of Helsinki, any participant must provide his/her consent to the study. For this reason, a general consent form is created and shared with all partners to allow each of them to update and translate it, in any case of need (Annex 1). The consent form contains general information about the project, the stage in which end-users' participant will be requested, with a quick description of the tasks to be completed. At the end of the document, the rights of the participants as well as the criteria for participation are specified. By dating and signing the document's last page participants give their consent to take part into the evaluation process.

How any pilot site deals with informed consent, final compensation, and ethical approval is described in the sections below.

#### 3.2.1 Italy (INRCA)

INRCA will submit the study protocol to its own Ethical Committee, in order to receive review and finally get the ethical approval.

The consent form will be delivered to the end user at recruitment stage, before asking any personal data and questionnaire. Before the planned evaluation, the consent form should be signed and returned to the researcher, if him/her want to be involved in the study process.

Due to Italian legislation, the participants will not receive money as a financial compensation for their contribution on the research activity, but laboratory exams and training on everyday technologies will be offered as compensation mean for the participation.

#### 3.2.2 Switzerland (HUG)

HUG will submit the study protocol to the Swiss Ethical Committee to get the ethical approval.

The consent form will be delivered to the end user at the recruitment stage, before asking any personal data and questionnaire. The consent should be signed and returned to the researcher before asking personal data and questionnaire. Participants will be informed that their data will be anonymous, that they are free not to answer all the questions, that they can withdraw at any time from the study without justification and that if they agree their data can be used for scientific publications.

Participants will receive money as financial compensation for their contribution on the research activity.

#### 3.2.3 Norway (KARDE)

In Norway, this project sorts under the NENT The Norwegian National Committee for Research Ethics in Science and Technology. For the purposes of the engAGE project (development of technology), we do not have to apply for an ethical approval. Consequently, Karde will not collect any personal medical information from the participants. Karde's WP4 leader, [name] has by The Norwegian Data Protection Authority been registered to be Karde's privacy ombud. She has the competency and capacity to monitor and supervise all ethical aspects connected to the engAGE project's Norwegian part. Inclusion and exclusion criteria

In this section, the inclusion and exclusion criteria for involving end users in engAGE lab test and field trials are described.

#### 3.2.4 Inclusion criteria

- PRIMARY END USERS (SMCI):
  - over 65 years old;
  - MoCA score 21 25;
  - MAC-Q ≥ 25;
  - Reisberg scale 2 4;
  - Clinical Frailty Scale score 1 3;
  - 4-items GDS score  $\leq$  1.
- SECONDARY END USERS (INFORMAL CAREGIVERS):
  - Over 18 years old;
  - Primary informal caregiver of the user (see the user at least 2 times per week);

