#### 3.2.5 Exclusion criteria

The exclusion criteria consist of

- Concomitant participation in other studies;
- Lack of written informed consent;
- Not meeting the inclusion criteria
- Previous diagnosis of dementia or other neurodegenerative diseases;
- Psychiatric illnesses that could affect cognitive functioning;
- Chronic neurological or systemic disorders not compensated pharmacologically that could affect cognitive functioning;

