#### 3.3.1 Italy (INRCA)

Regarding the recruitment channel, Italian partners will use the contact list of their neurology unit and Alzheimer day-care centre to communicate with potential participants of previous projects and initiatives, as well as with other people who might be interested in contributing to the project evaluations. This method makes possible to be in contact with clients met before and with whom a relationship of trust has been already established.

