#### MONTREAL COGNITIVE ASSESSMENT (MOCA)

#### **REISEBERG SCALE**

Level	Clinical characteristics
1 No cognitive decline	No subjective complaints of memory deficit. No memory deficit evident on clinical interview.
2 Very mild cognitive decline (Age Associated Memory Impairment)	Subjective complaints of memory deficit, most frequently in following areas: (a) forgetting where one has placed familiar objects; (b) forgetting names one formerly knew well. No objective evidence of memory deficit on clinical interview. No objective deficits in employment or social situations. Appropriate concern with respect to symptomatology.
3 Mild cognitive decline (Mild Cognitive Impairment)	Earliest clear-cut deficits. Manifestations in more than one of the following areas: (a) patient may have gotten lost when traveling to an unfamiliar location; (b) coworkers become aware of patient's relatively poor performance; (c) word and name finding deficit becomes evident to intimates; (d) patient may read a passage or a book and retain relatively little material; (e) patient may demonstrate decreased facility in remembering names upon introduction to new people; (f) patient may have lost or misplaced an object of value; (g) concentration deficit may be evident on clinical testing. Objective evidence of memory deficit obtained only with an intensive interview. Decreased performance in demanding employment and social settings. Denial begins to become manifest in patient. Mild to moderate anxiety accompanies symptoms.
4 Moderate cognitive decline (Mild Dementia)	Clear-cut deficit on careful clinical interview. Deficit manifest in following areas: (a) decreased knowledge of current and recent events; (b) may exhibit some deficit in memory of ones personal history; (c) concentration deficit elicited on serial subtractions; (d) decreased ability to travel, handle finances, etc. Frequently no deficit in following areas: (a) orientation to time and place; (b) recognition of familiar persons and faces; (c) ability to travel to familiar locations. Inability to perform complex tasks. Denial is dominant defense mechanism. Flattening of affect and withdrawal from challenging situations frequently occur.

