**Total score** 

#### **CLINICAL FRAILTY TEST**

1	Ì	Very Fit - People who are robust, active, energetic and motivated. These people commonly exercise regularly. They are among the fittest for their age.
2	Ţ	Well - People who have no active disease symptoms but are less fit than category 1. Often, they exercise or are very active occasionally, e.g. seasonally.
3	Ì	Managing Well - People whose medical problems are well controlled, but are not regularly active beyond routine walking.
4	A	Vulnerable - While not dependent on others for daily help, often symptoms limit activities. A common complaint is being "slowed up", and/or being tired during the day.
5		Mildly Frail - These people often have more evident slowing, and need help in high order IADLs (finances, transportation, heavy housework, medications). Typically, mild frailty progressively impairs shopping and walking outside alone, meal preparation and house work.
6		Moderately Frail - People need help with all outside activities and with keeping house. Inside, they often have problems with stairs and need help with bathing and might need minimal assistance (cuing, standby) with dressing.
7	A.	Severely Frail - Completely dependent for personal care, from whatever cause (physical or cognitive). Even so, they seem stable and not at high risk of dying (within $\sim 6$ months).
8		Very Severely Frail - Completely dependent, approaching the end of life. Typically, they could not recover even from a minor illness.
9	6	Terminally III - Approaching the end of life. This category applies to people with a life expectancy < 6 months, who are not otherwise evidently frail.

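### The Reisberg range admits stage 4, which the trial's own form labels mild dementia, and the exclusion bars only dementia already diagnosed

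*Combined protocol and SAP*

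**What the plan says.** The study population is seniors with MCI (section 1.1, and the primary end users in section 3.2.4). One inclusion criterion in 3.2.4 is "Reisberg scale 2 4". The range sign is lost in the text, but section 3.5 names stages 2, 3 and 4 one by one, so it reads as 2 to 4. Section 3.5 describes stage 3 as mild cognitive impairment and stage 4 as moderate cognitive decline, without mentioning dementia.

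On the Reisberg form in Annex 3, the stage 4 row begins "4 Moderate cognitive decline (Mild Dementia" and includes the statement "Denial is dominant defense mechanism". The stage 3 row carries the MCI label and says that denial is starting to show.

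The matching exclusion in 3.2.5 is "Previous diagnosis of dementia or other neurodegenerative diseases". Item 23 of the recruitment questionnaire likewise refers to diagnosed dementia.

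The primary outcome is MAC-Q (section 3.4), a self-report on which higher scores mean worse memory (section 3.5). Hypothesis 1 in section 3.7 compares it between the experimental group (EG) and the control group (CG), and also before and after within the EG.

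**The concern.** The passages that define who is eligible do not agree. A reader of section 3.5 alone would not see that the range reaches a stage that the rater's form calls dementia. The exclusion does not close the gap, because it looks back to an existing diagnosis and says nothing about what the recruitment assessment itself finds.

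Two things are at stake. First, a result from a sample that includes stage 4 seniors could not be attributed cleanly to MCI. Second, the primary outcome depends on the participant's insight, and the trial's own form says insight fades across the later part of the admitted range. A senior who becomes less aware of memory problems during six months will score lower on MAC-Q, which reads as improvement. That can mislead in a before/after comparison without a control, and such a comparison is planned.

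**Working it through.** **Can a stage 4 senior enter?** Take a senior with no earlier dementia diagnosis who is first staged 4 at recruitment.

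1. Reisberg 2 to 4 (3.2.4): met.
2. Dementia exclusion (3.2.5 and item 23 of the form): not triggered, because there is no previous diagnosis.
3. MoCA 21 to 25, Clinical Frailty Scale (CFS) 1 to 3 and MAC-Q of at least 25 (3.2.4): each makes entry less likely. None refers to the Reisberg stage, and none rules it out.

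So entry is possible under the rules as written.

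**Norway.** Table 5 tags MoCA for two countries only, which reads as Italy and Switzerland. Section 4.3.3 says that diagnoses of MCI or dementia will not be asked for in Norway. There, neither the MoCA criterion nor the diagnosis exclusion can work as written. Table 2 gives Norway 8 to 10 EG seniors and at least 10 controls, so at least 18 to 20 seniors.

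**How far can MAC-Q move through insight alone?** Five items score 1 to 5, and the last scores double (2 to 10). If every item is answered in category c, the total is 5c + 2c = 7c.

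- Lowest and highest totals: 7 × 1 = 7 and 7 × 5 = 35.
- Somewhat poorer on every item (c = 4): 5 × 4 + 8 = 28.
- About the same on every item (c = 3): 5 × 3 + 6 = 21.
- One category lower on every item: 28 − 21 = 7 points of apparent improvement, from above the cut-off of 25 to below it.

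**Effect on the EG mean (illustration).** The documents give neither the share f of participants who lose insight nor the shift s in their score. Assume f from 10% to 30% and s from 3.5 to 7 points. The mean falls by f × s:

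- smallest: 0.10 × 3.5 = 0.35 points;
- largest: 0.30 × 7 = 2.1 points.

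**Effect on EG versus CG.** If the shift is equally common in both arms, its expected contribution to the difference is 0. Only chance imbalance remains, with standard error s × √[f(1 − f)(1/n₁ + 1/n₂)]. Assume n₁ = 50 and n₂ = 30, which sum to the 80 in section 3.1:

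- f = 0.10, s = 3.5: 3.5 × √(0.09 × 0.0533) = 0.24 points;
- f = 0.30, s = 7: 7 × √(0.21 × 0.0533) = 0.74 points.

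The systematic error therefore belongs to the within-EG reading.

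**The case against.** The strongest reply is that the criteria in 3.2.4 apply jointly. A senior who already denies memory problems is unlikely to reach a MAC-Q of 25, and MoCA and CFS narrow entry further. Section 3.1 also randomises and calls the study a small pilot with only a partial evaluation of effectiveness, and section 3.7 lists the EG versus CG comparison first. All of this stands. It makes stage 4 entrants fewer and protects the randomised contrast, but it does not make the range, the form and the exclusion agree.

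It is also fair to say that loss of insight is not peculiar to stage 4. The form places the start of denial at stage 3, so ending the range lower would reduce the problem without removing it. MoCA is repeated at T2 at the sites of 40 to 45 of the 48 to 55 EG seniors, so some objective data will exist. However, MoCA is not among the outcomes in 3.4 and is not part of hypothesis 1. The correlations of MAC-Q subscales with other scales in 4.1 are aimed at acceptability.

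A reader might infer more than the documents support:

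- That stage 4 contradicts the frailty criterion. The form describes reduced ability with travel and finances, while CFS 5 describes people who "need help in high order IADLs (finances, transportation, heavy housework, medications". These are close but not the same, so this is a tension rather than a contradiction.
- That "stratifying for MCI" in section 3.7 shows that people beyond MCI are expected. The phrase is undefined. It could mean severity, or could refer to stage 2, which the form also places outside its MCI label.
- That recruiting in Italy through the "contact list of their neurology unit and Alzheimer day-care centre" means dementia will be enrolled. Anyone on that list with a diagnosis is excluded, and the channel also reaches other interested people.

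**Conclusion.** The point holds as an inconsistency in eligibility with a limited consequence for the analysis. As written, a senior first staged 4 at recruitment can enter a trial meant for MCI, and this is easier in Norway. How many would do so cannot be derived.

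It would go too far to say that the trial will read worsening as benefit. That requires insight to fall during follow-up in people who reported enough memory loss to enter, and it produces a systematic error only in the intra-group comparison. The EG versus CG contrast is affected only if loss of insight or dropout differs by arm, and the documents say nothing either way about that. The 7-point example follows from the MAC-Q scoring. The range of 0.35 to 2.1 points for the EG mean rests on assumed shares and shifts.

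Severity is moderate.

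**What to change.** 1. Reconcile sections 3.2.4, 3.2.5 and 3.5 with the Annex 3 form, so that the Reisberg range and the dementia exclusion both agree with the MCI target population. Which stages belong is a clinical decision for the sponsor.
2. Word the exclusion so that it covers dementia-level staging found at recruitment as well as a previous diagnosis, and state how it is applied in Norway.
3. Use the form's stage 4 label in section 3.5.
4. Report MAC-Q with and without any stage 4 seniors enrolled. The Reisberg stage is scheduled at recruitment (Table 5), so selecting on it does not select on anything that happened after allocation.
5. State in 3.7 and 4.1 that the MAC-Q conclusion rests on the EG versus CG contrast, with the intra-group change as descriptive. The test sentence in 4.1 now names only pre and post conditions.

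The cost is a wording amendment, one extra sensitivity analysis and possibly the loss of a few candidates.
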